6.0 Legal and Ethical Considerations

The Principal Investigator and the study staff are responsible for conducting this study in accordance with the applicable principles which have their origins in the Declaration of Helsinki, ICH, GCPs, and all other applicable laws and regulations.

- 6.1 Institutional Review Board / Independent Ethics Committee (IRB/IEC) Approval
 - This protocol, the Informed Consent, relevant supporting information, and all types of subject recruitment or advertisement information must be approved by the appropriate IRB/IEC before the study is initiated. Any amendments to the protocol must also be approved, where necessary, by the IRB/IEC prior to implementing changes in the study. The IRB/IEC used must comply with current regulations and GCP.
 - > The investigator's responsibilities regarding the IRB/IEC are as follows:
 - Obtaining IRB/IEC approval of the protocol, informed consent, and any advertisements to recruit subjects prior to their use.
 - Obtaining IRB/IEC approval for any protocol amendments and Informed Consent revisions before implementing the changes.
 - Providing the IRB/IEC with any required information before and during the study.
 - Submitting progress reports to the IRB/IEC as required.
 - Notifying the IRB/IEC within 10 days (unless required sooner by IRB/IEC) of all serious and unexpected AEs related to the study medications that are reported to you by the Sponsor. The investigator is responsible for updating the IRB/IEC on the progress of the study and of any changes made to the protocol at least once a year or at regular intervals as required by the IRB/IEC. The investigator must also keep the IRB/IEC informed of any AEs, according to the IRB/IEC policy.
- 6.2 Subject Information and Informed Consents
 - Informed consent (per 21 CFR, Part50) and Health Insurance Portability and Accountability Act of 1996 authorization (per 45 CFR, Part 164) will be obtained from each subject and their caregiver prior to conducting/ obtaining any study-related assessments including the discontinuation of any study prohibited medications. An informed consent document that includes both information about the study and the consent from will be prepared and given to the subject. The document must be in a language understandable to the subject and must specify who informed the subject.
 - The investigator's draft Informed Consent must be reviewed by the Liver Institute, prior to IRB/IEC submission for approval.
 - If, during the study, the subject's protected health information (PHI) is to be used or disclosed in a manner that is inconsistent with the Informed Consent, the investigator must obtain a new authorization from the subject or a waiver of authorization from the IRB/IEC or privacy board, as applicable. If the Informed Consent is amended during the study, the investigator must follow all applicable regulatory requirements pertaining to

approval of the amended Informed Consent by the IRB/IEC and use of the amended form (including for ongoing subjects).

The Informed Consent documents the study-specific information the investigator provides to the subject and the subject's agreement to participate.

6.3 Confidentiality

- Anonymity of subjects participating in this study will be maintained. Every effort will be made to maintain the confidentiality of documents that identify the subjects by name (e.g., signed informed consent document and patient data).
- The investigator and other study site personnel will keep confidential any information related to this study and all data and records generated in the course of conducting the study, and will not use the information, data, or records for any purpose other than conducting the study. These restrictions do not apply to:
 - 1. Information which becomes publicly available through no fault of the investigator or study site personnel
 - 2. Information which it is necessary to disclose in confidence to an IRB/EC solely for the evaluation of the study

or

3. Study results which may be published. If a written contract for the conduct of the study which includes confidentiality provisions inconsistent with this statement is executed, that contract's confidentiality provisions shall apply rather than this statement.

6.4 Record Retention

Essential documents as described above should be retained for one of the following time periods: At least 2 years after conclusion of the study.

6.5 Publication Policy

Institution and the investigator shall have the right, consistent with academic standards, to publish or present the results of the study, provided such publication or presentation does not disclose confidential information.

6.6 Financial Support

> This study is funded by the Liver Institute PLLC.

7.0 Discussion and Expected Challenges

- Several challenges stand in the way towards complete Hepatitis C eradication. In addition to lack of public awareness leading to low screening percentage, only about 26.1% of the HCV+ population receive treatment.
- During the gap periods of the study the project coordinator will communicate with patients and providers to facilitate the process of treatment. However, several challenges like insurance and access to healthcare might not be inevitable, making it unlikely to increase the treatment rate significantly. On the other hand, the total number is expected to proportionally increase with the number of screened individuals.
- Increasing the public awareness will likely result in a sustained increase in screening rates and gradual improvement in treatment availability and access. Therefore, and through utilizing more efforts the treatment rates can be expected to increase over the upcoming years, moving closer towards our goal of HCV eradication.

8.0 Appendix

8.1 Email Message Template "Dear Patient Name,

My name is coordinator name, and I am the coordinator of a Hepatitis C Outreach program designed to increase awareness and promote screening of all the Arizona population for a goal of improved total community health.

Hepatitis C is a widespread, possibly asymptomatic disease affecting millions of the population and could result in severe liver damage and even mortality if left untreated. While historically people with risk factors are screened, these standards left millions undiagnosed and therefore contributed to making it an epidemic. We encourage you to go over the attached infographic for more information on hepatitis C.

To avoid complications of this treatable condition, we have collaborated with Sonora Quest Laboratories in the state of Arizona to provide screening services, free of charge, to all individuals in the state. If needed, our research team will contact you for further links to care and treatment. We ask you to please use the promotional code at any Sonora Quest to get your Hepatitis C screening. click on the link below to select your preferred Sonora Quest and schedule an appointment.

'Link'

Best regards,

'Attached infographic'

Contact Information"

8.2 Text Message Template

"We are reaching out to you regarding our Hepatitis C eradication program. Hepatitis C is widespread, possibly asymptomatic disease and, if left untreated, could result in serious liver damage. Our goal is to increase awareness and promote screening of all individuals residing in Arizona. If interested, use the code below to get free screening at any Sonora Quest labs."

8.3 FAQ Section

- 1. Is hepatitis C curable?
 - a. Yes. With current and evolving antiviral treatments and liver transplants, 95% of hepatitis C cases are treated.
 - 2. Does it cause any complications?
 - a. Hepatitis C is a progressive infection and can lead to cirrhosis (scarring of the liver tissue), liver cancer and liver failure.
 - 3. Is hepatitis C fatal?

LI-HEPC-AZ V1.0 CONFIDENTIAL

- a. Hepatitis C can be fatal if left untreated as it can lead to cirrhosis, HCC (liver cancer), and several other complications.
- 4. Am I at risk?
 - a. You are considered at risk if you:
 - i. Were born between 1945 and 1965.
 - ii. Had a blood transfusion or organ transplant before the year of 1992
 - iii. Received clotting factors prior to 1987
 - iv. Received hemodialysis for a long period of time
 - v. Were born to a mother with hepatitis C
 - vi. Have piercings or tattoos
 - vii. Have a risky sex life
 - viii. Have injected or inhaled illicit drugs
 - ix. Have HIV (Human Immunodeficiency Virus)
 - x. Work in healthcare and have been exposed to infected blood
- 5. Where can I get screened?
 - a. Screening will be provided at any of our collaborating pharmacies in the State of Arizona.
- 6. What will be the next step if I test positive?
 - a. In case the antibody test is positive, further testing will be done and you will be linked to specialists for treatment.
- 7. Can I get screened if I do not have insurance?
 - a. Yes. Screening will be provided free of charge at any of our collaborating pharmacies.
- 8. Are there any lifestyle changes I need to follow in case of Hepatitis C diagnosis?
 - a. Some lifestyle changes that could slow the progression of Hepatitis C are to stop drinking alcohol, avoid medications that can cause liver damage including some herbal supplements and over-the-counter drugs.

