The study will focus on various methods of communication to reach the **Methods:** population of Arizona from the most prevalent counties to lowest prevalence. The study is organized into phases focusing on the various communication methods beginning with direct communication through mass text messages and mass emails followed by indirect communication through social media (YouTube, Facebook), newspaper, radio, Alcoholics Anonymous meetings, Narcotics Anonymous meetings, and homeless shelters. Each phase will consist of four cycles of a monthly intervention period in which communication will be active and a two-month gap that will be used to assess effectiveness of the communication method. Subjects will receive information on HCV, contact information for the study coordinator at the Liver Institute PLLC to address questions or concerns, and a code that will allow them to receive a free HCV screening test at their local Sonora Quest Lab. This code can be used at the time of receipt or a few months later, whenever the subject is ready for testing. This timeline allows to enhance subject compliance. The results from Sonora Quest Lab will be transmitted to the study coordinator at the Liver Institute PLLC and depending on the subject's insurance status will link the subject to a treatment center. Ideally it will be their primary care physician but if the subject does not have one then it will be the closest treatment center. Alternatively, the Liver Institute PLLC is also equipped to provide telemedicine appointments to evaluate the subject and provide treatment depending on insurance status. Those that are uninsured will be provided with available options for treatment. All subjects will receive information on the disease to reduce transmission and encourage friends/family to get tested. This study will function on a version of the test-and-treat approach to help reduce the spread of HCV in the Arizona population. **Results:** The study will allow us to obtain diagnostic rates for each communication method as well as the number of HCV positive individuals that are linked to care for treatment. By comparing diagnostic rates between communication methods, we can identify the most successful method to utilize for a bigger subject outreach. Additionally, by determining the rates of HCV positive individuals linked to care, we can identify deficits in the treatment of screened individuals. These components taken together will allow us to evaluate the overall success of our study.

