3.0 Investigational Plan

3.1 Study Design

- This is a prospective study performed over a 45-month period. The principal design plan will follow Figure 3 below.
- The study design is based on HCV prevalence order, which was determined based on statistical data from the Arizona Department of Health Services and rate of Hepatitis C per 100,000 (Figure 4). High prevalence counties (123+ cases per 100,000) including La Paz, Mohave, and Yavapai with a total targeted population of 391,999 individuals. Medium-prevalence Counties (101-123 cases per 100,000) are Coconino, Gila, Greenlee, Maricopa, Pima and Pinal with total targeted population of 4,724,421. Low-prevalence counties (<101 per 100,000) including Apache, Cochise, Graham, Navajo, Santa Cruz, and Yuma with a population of 490,388.

- For the initial 9 months the study will utilize direct communication methods (email and text messages) to reach high prevalence areas (Month 1-6), medium prevalence areas (Months 7- 12), and low prevalence areas (Month 13-18).
- The second phase of the study will utilize indirect communication methods (Newspapers and Radio advertisements) and similarly target areas of high prevalence (Month 12-24), medium prevalence (Month 25-30) and low prevalence (Month 31-36).
- The third and last phase is detected for shelter visits and homeless education in high prevalence areas (Month 37-39), mid-prevalence areas (Month 40-42) and low prevalence areas (Month 43- 45).
- This program will follow a streamline cascade of care with three complementary, consecutive portions: Patient education during intervention periods, connection to appropriate care and treatment during gap periods (Figure 3).
- The person responsible for conducting and implementing the project will be the program coordinator. The coordinator will be responsible for responding to calls or emails regarding the study in reference to the FAQ in Appendix 8.3. One hour daily, 5 days per week will be dedicated to answering emails and responding to voice messages or calls. The number of hours will be adjusted according to project performance and needs.

Phase 1: Direct Communication

1. Direct Customized Email Messages

Email messages are customizable and tailored to individual people. The expected response rate as compared to similar healthcare content is about 2%, 112,136 of our targeted group.

a. Generating Email List

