3.4 Population Screening

Screening Promotion

A time limited screening test promotion code, specific to educational outreach methods, will be obtained from Sonora Quest Laboratories and advertised in both direct and indirect communication methods of the educational program. Interested individuals would be required to present a specific promotional code and sign the Informed Consent Form.

Screening Locations

Screening will take place in all branches of Sonora Quest Laboratories over the state of Arizona. Patients will have the opportunity to present at any of the locations and get free screening regardless of their insurance coverage or whether they are considered at risk or not.

Informed Consents

The study, expectations and rights will be explained to patients. Informed consents will be obtained electronically by the screening team to perform anti- HCV test, to share personal information and test result with Liver Institute study investigator team, and to agree to discuss treatment options if HCV test become positive. Consents will be sent to the Liver Institute PLLC where they will be stored in an encrypted electronic data capture system as per Western Institutional Review Board (WIRB) guidelines.

Clinical Parameters

Demographics data and contact information will be recorded for each patient in Sonora Quest Laboratories data system as per their guidelines. Clinical and relevant history pertaining to hepatitis C including diabetes and existing conditions will be collected by study team from HCV positive individuals.

LI-HEPC-AZ V1.0 CONFIDENTIAL ➢ Screening

Screening will be conducted by members of the Sonora Quest Laboratories with ELISA IV antibody test with reflex to HCV PCR test to confirm the diagnosis. Patients will be contacted with their test results by a member of the research team, as well as by Sonora Quest.

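### The FAQ that guides the coordinator's replies places screening at collaborating pharmacies, while the rest of the protocol places it only at Sonora Quest

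*Protocol*

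**What the plan says.** Two answers in Appendix 8.3 concern the place of screening. Item 5, on where to go, reads "Screening will be provided at any of our collaborating pharmacies in the State of Arizona". Item 7, on people without insurance, reads "Screening will be provided free of charge at any of our collaborating pharmacies".

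The rest of the protocol names a different place:

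- **Synopsis, Methods:** subjects receive "a code that will allow them to receive a free HCV screening test at their local Sonora Quest Lab".
- **Section 3.4, Screening Locations:** "Screening will take place in all branches of Sonora Quest Laboratories over the state of Arizona".
- **Section 3.4, Screening:** "Screening will be conducted by members of the Sonora Quest Laboratories".
- **Section 3.4, Screening Promotion:** the promotional code is "specific to educational outreach methods, will be obtained from Sonora Quest Laboratories".
- **Section 3.4, Informed Consents:** "Informed consents will be obtained electronically by the screening team to perform anti- HCV test".
- **Appendices 8.1 and 8.2:** the email and text templates both tell the recipient to use the code at any Sonora Quest location.

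Section 3.1 gives the FAQ its function: "The coordinator will be responsible for responding to calls or emails regarding the study in reference to the FAQ in Appendix 8.3".

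**The concern.** The FAQ gives one answer to the most practical question a willing person can ask, and the rest of the protocol gives another. The difference is more than a label. In the protocol, the code, the test and the return of results all run through Sonora Quest. Nothing equivalent is described for a pharmacy.

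Patients screened is a primary endpoint (Section 2.2), and success is defined by a monthly count of tests (Section 5.3). Someone who contacts the coordinator, is told to go to a pharmacy and acts on that would not be tested under the study and would not enter the count. Item 7 gives the same answer to uninsured people, whom Section 3.4 includes by offering free screening regardless of coverage.

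**Working it through.** No sample size, power or error rate is involved. The check compares the places where the protocol names a screening site, then traces what a subject needs in order to be counted.

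**Step 1. Where each part of the protocol places screening**

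| Place in protocol | Site named |
|---|---|
| Synopsis, Methods | Sonora Quest |
| Section 3.4 | Sonora Quest, all branches |
| Appendix 8.1 (email) | Sonora Quest |
| Appendix 8.2 (text) | Sonora Quest |
| Appendix 8.3, item 5 | Collaborating pharmacies |
| Appendix 8.3, item 7 | Collaborating pharmacies |

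Four places agree with each other. The two FAQ answers agree only with each other. Both are intact sentences, so damage in reading the PDF does not explain the conflict.

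**Step 2. What a subject needs in order to be counted**

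| Requirement | Sonora Quest | Pharmacy |
|---|---|---|
| Promotional code | Supplied by Sonora Quest (Section 3.4) and used there (synopsis) | Not described |
| Signed consent, also an inclusion criterion (Section 4.1) | Taken by the screening team (Section 3.4) | Not described |
| Antibody test with reflex PCR | Run by Sonora Quest staff (Section 3.4) | Not described |
| Result sent to the coordinator | From Sonora Quest (synopsis) | Not described |

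As the text stands, a person who follows the FAQ reaches a site with no described route into the study. The templates say nothing about consent. That element rests on Section 3.4 alone.

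**Step 3. Who would depend on the FAQ answer**

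- **Email and text:** the message itself names Sonora Quest.
- **YouTube:** the videos are planned to link to screening locations (Section 3.1).
- **Newspaper:** the infographic is planned to give next steps (Section 3.1), but its wording is not shown.
- **Radio:** Section 3.1 lists a short introduction, the rationale and the coordinator's contact details. It lists no site.

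Radio is therefore the channel where reliance on the coordinator's reply is most plausible. Section 3.4 does say that the code will be advertised in indirect methods as well, so even a radio listener may hear of Sonora Quest.

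**Step 4. Can the size be computed?**

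The success threshold reproduces: 53,580 / 12 = 4,465 tests per month, and 2 × 4,465 = 8,930. That gives the scale of the endpoint but not of the loss. The number missed would be

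contacts per month × share asking where to go × share given the FAQ answer uncorrected × share who act on it and never reach Sonora Quest.

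The protocol gives none of these four terms. The nearest figure is the coordinator's time, 1 hour × 5 days = 5 hours a week (Section 3.1). It is stated to be adjustable and does not translate into a number of contacts. No estimate follows.

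**The case against.** The best defence is that the FAQ wording is probably left over from another plan and would do little harm:

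- The FAQ names no particular pharmacy, so a caller would have to ask which one. The coordinator who answers also signs an email that names Sonora Quest and links to booking there.
- Section 3.1 makes the FAQ a reference. It does not require that it be read out word for word.
- Several channels carry the right location, or are planned to carry next steps, without the FAQ.
- Section 6.1 requires IRB approval of recruitment material before use, so the slip may be caught there.
- No endpoint definition, analysis or threshold changes.

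Most of this stands as a limit on the consequence. It does not remove the contradiction: the protocol's designated reference for answering enquiries gives a site that the protocol does not otherwise provide for, and gives it twice.

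Two stronger readings are tempting. A reader might infer that subjects will be lost in some sizeable monthly number. Any such number needs an assumed share of callers, and the protocol supplies no basis for one. A reader might also infer that the comparison between communication methods is biased against channels that generate calls. The protocol does not show how many contacts each channel would produce or what the newspaper and radio material will finally say, so that remains speculation.

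**Conclusion.** The inconsistency is real and should be corrected. FAQ items 5 and 7 conflict with the synopsis, Section 3.4 and both message templates on where screening takes place, and Section 3.1 puts the FAQ to use in answering subjects. The documents support saying that a person relying on that answer could be misdirected and so missed from the primary endpoint. They do not support saying that subjects will be lost, or how many.

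The conclusion rests on two assumptions. First, Section 3.4 states the intended arrangement, as its agreement with the synopsis and both templates suggests. Second, no pharmacy arrangement is described in the parts that could not be read, namely the figures and some appendix material after the Section 8.5 heading. If either assumption fails, the texts still need to be reconciled, because the templates and Section 3.4 would then be incomplete. The fault lies in participant-facing material and does not undermine the design.

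**What to change.** Reword items 5 and 7 of Appendix 8.3 to say that free screening is available at any Sonora Quest branch on presenting the promotional code, as in Section 3.4. Do this before the recruitment material goes to the IRB. The synopsis still lists the IRB number as pending, so the correction can travel with the first submission. The cost is two sentences.

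If pharmacies are really intended as screening sites, add them to Section 3.4 with their own arrangements for code redemption, testing, consent and transfer of results to the coordinator, and align the email and text templates. That is a larger change, because it adds a second type of site to the study's procedures.

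In either case, check the newspaper, YouTube and radio content against Section 3.4 so that all subject-facing material names the same place.
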